Cover Page

Official Title: Morning Light Treatment at Home to Reduce PTSD Symptoms

Document Type: Study Protocol with Statistical Analysis Plan (SAP)

Document Date: 04/19/2018

NCT Number: NCT03513848

Study Protocol

The study will take 36 days and consist of the following:

WEEK 1 (Days 1-7):

- A home sleep section with a wrist monitor that records motion and light.
- Daily logs of activities, sleep, nightmares, and medications.

WEEKS 2 – 6 (Days 8-36):

- Daily logs of activities, sleep, nightmares, and medications
- A home sleep section with a daily morning light treatment the participant self-administers using the Re-timer light device. Participant is randomized (assigned by chance) to a placebo (inactive) Re-timer or active Re-timer. Participant continues to wear the wrist monitor that records motion and light.
- Weekly lab visits to complete questionnaires on days 8, 15, 22, 29, and 36. During these visits, participants are breathalyzed and we review the data from daily logs and wrist monitor. We will also review if participants followed the light treatment schedule.

During the home sleep sections of the study, you will sleep at your usual sleep times and fill out a few daily questionnaires.

The lab visits will consist of setting up or downloading data from the wrist monitor, completing questionnaires on a computer, and training sessions on how to best use the Re-timer light device for light therapy every morning.

Statistical Analysis Plan

- We will conduct a t-test to evaluate difference in PTSD symptom changes from pre- to post-treatment between the active and placebo group. We will calculate the effect size of the difference between the groups.
- We will conduct a t-test to evaluate difference in depression symptom changes from pre- to post-treatment between the active and placebo group. We will calculate the effect size of the difference between the groups.
- We will evaluate actigraphy data to provide descriptive information regarding treatment compliance.

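### Both efficacy tests are t-tests on change; adjusting for the pre-treatment score may gain precision at a small, bounded cost

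*Combined protocol and SAP*

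**What the plan says.** The Statistical Analysis Plan has three bullets. The first reads "We will conduct a t-test to evaluate difference in PTSD symptom changes from pre- to post-treatment between the active and placebo group". The second applies the same test to the other outcome: "We will conduct a t-test to evaluate difference in depression symptom changes from pre- to post-treatment between the active and placebo group". Each adds "We will calculate the effect size of the difference between the groups", without naming the standard deviation to be used as denominator. The third bullet makes actigraphy descriptive, for compliance.

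The Study Protocol section, under Weeks 2 – 6, says "Participant is randomized (assigned by chance) to a placebo (inactive) Re-timer or active Re-timer" and gives no allocation ratio. It also lists "Weekly lab visits to complete questionnaires on days 8, 15, 22, 29, and 36". No visit is named as the source of the pre- or post-treatment score, but a change cannot be computed without a pre-treatment score. Neither section mentions a covariate, a regression or a mixed model.

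**The concern.** A two-sample t-test on change does use the pre-treatment score, but with its coefficient fixed at 1. The coefficient that minimises residual variance is the slope of post on pre, which is ρ·s₁/s₀ (ρ the within-arm pre-post correlation, s₀ and s₁ the pre- and post-treatment SDs). If that slope is below 1, the change score over-corrects for the pre-treatment value and carries avoidable noise.

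Active versus placebo is the question the trial asks. Where the slope is clearly below 1 and the arms are not very small, the planned tests give wider intervals and less power than the same data allow. This affects both efficacy outcomes. The greater sensitivity of the change score to chance baseline imbalance is this same excess variance and is not a second harm.

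**Working it through.** **Inputs.** From the document: two randomised arms, and a t-test on change for each outcome. Not in the document, so assumed: 1:1 allocation, two-sided 5%, complete data, bivariate normal scores with a common covariance matrix, a true difference of 0.6 pre-treatment SD, and ranges for n per arm, ρ and k = s₁/s₀. The plan has no power or sample-size figure to reproduce.

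**Step 1: large-sample variance.** Set the pre-treatment SD to 1.

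- Change score: 1 + k² − 2ρk
- ANCOVA: k²(1 − ρ²)
- Difference: (1 − kρ)², which is never negative and is zero only when the slope kρ equals 1

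With k = 1 the ratio ANCOVA/change is (1 − ρ²)/(2 − 2ρ) = (1 + ρ)/2. Worked case with unequal SDs: at k = 1.2 and ρ = 0.5, the change variance is 1 + 1.44 − 1.20 = 1.24, the ANCOVA variance is 1.44 × 0.75 = 1.08, and the ratio is 0.87.

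| k | ρ = 0.5 | ρ = 0.7 | ρ = 0.9 |
|---|---|---|---|
| 1.0 | 0.75 | 0.85 | 0.95 |
| 1.2 | 0.87 | 0.97 | – |
| 1.4 | 0.94 | 1.00 | – |

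**Step 2: power in finite samples.** The t-test on change uses the noncentral t with 2n − 2 df. ANCOVA uses the noncentral t with 2n − 3 df and a variance multiplied by 1 + T²/(2n − 2), averaged over T ~ t(2n − 2). T is the standardised chance imbalance in the pre-treatment score. For example, with n = 20, k = 1 and ρ = 0.5, the change variance is 1, the standard error is √(2/20) = 0.316, and the noncentrality is 0.6/0.316 = 1.90, giving 45.6%. For ANCOVA the variance is 0.75 before inflation, giving 55.8%.

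| n per arm | ρ | k | t-test on change | ANCOVA |
|---|---|---|---|---|
| 6 | 0.5 | 1.0 | 15.6% | 17.6% |
| 10 | 0.5 | 1.0 | 24.6% | 29.6% |
| 20 | 0.5 | 1.0 | 45.6% | 55.8% |
| 30 | 0.5 | 1.0 | 62.8% | 74.4% |
| 10 | 0.7 | 1.0 | 37.5% | 40.7% |
| 20 | 0.7 | 1.0 | 66.5% | 72.3% |
| 30 | 0.7 | 1.0 | 83.9% | 88.7% |
| 20 | 0.5 | 1.2 | 38.3% | 41.9% |
| 20 | 0.7 | 1.2 | 56.4% | 56.7% |
| 6 | 0.8 | 1.0 | 31.8% | 31.5% |
| 6 | 0.9 | 1.0 | 55.5% | 52.6% |
| 6 | 0.9 | 1.1 | 49.9% | 45.4% |
| 10 | 0.7 | 1.4 | 24.6% | 23.4% |
| 20 | 0.7 | 1.4 | 45.6% | 44.6% |
| 20 | 0.8 | 1.2 | 72.7% | 71.6% |

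The last six rows are losses for ANCOVA. In the last four, the slope is 0.90 to 0.99 or the arms are very small, or both; the two equal-SD losses need 6 per arm and ρ of 0.8 or more.

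**Step 3: the most ANCOVA can lose.** Set the slope to exactly 1, so that both residual variances are equal, and maximise the power loss over all effect sizes.

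| n per arm | Largest power loss | Mean interval wider by at most | Break-even ρ for interval width (k = 1) |
|---|---|---|---|
| 6 | 5.5 points | 7.0% | 0.75 |
| 10 | 2.8 points | 3.3% | 0.87 |
| 20 | 1.2 points | 1.4% | 0.94 |
| 30 | 0.8 points | 0.9% | 0.96 |

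ANCOVA gives the narrower mean interval below the break-even ρ.

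**Step 4: checks.** Simulation of 21 settings (200,000 trials each, 6 to 40 per arm) agreed with the exact power to within 0.3 points. Type I error was 4.9% to 5.2% for both methods, and both estimators averaged 0.598 to 0.601 for a true 0.6.

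**The case against.** The strongest reply is that nothing here is wrong. The planned test matches its stated question, and it is valid under randomisation. Replacing it with another valid test is a preference whose benefit in this trial cannot be shown, because no sample size, SD, correlation or allocation ratio is given. That stands as a limit: the algebra is certain, but the size of the gain is not.

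A second reply is that the asymmetry between gain and cost fails in very small arms. This is partly right. At 6 per arm, with gain and loss both maximised over effect size and equal SDs, the gain is 12.9 points at ρ = 0.3, 6.9 at 0.5 and 1.6 at 0.7, against a possible loss of 5.5. Below 6 per arm the largest loss grows, to about 7.2 points at 5 and 10.6 at 4. The case is clear from roughly 10 to 20 per arm upward, and the document does not say that the trial is that large.

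Third, the large-sample guarantee needs 1:1 allocation or a common slope. With slopes that differ by arm (0.2 to 1.4 examined), the variance ratio never exceeded 1.00 at 1:1 but reached 1.28 at 2:1.

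Finally, the undefined effect-size denominator is a reporting gap under either test and adds no weight to the case for ANCOVA. Nor are the pre and post visits named, but that gap affects both analyses equally.

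**Conclusion.** The point holds, as a cheap improvement to a valid plan. At 1:1 allocation the t-test on change is never more precise in large samples than ANCOVA on the same two scores, and it is less precise whenever the slope of post on pre differs from 1. At 20 per arm, under the stated assumptions with equal SDs, ANCOVA adds 10.2 points of power at ρ = 0.5 (55.8 − 45.6) and 5.8 at ρ = 0.7 (72.3 − 66.5), against a largest possible loss of 1.2. The advantage disappears when the slope is near 1. It can reverse slightly there, or when arms are very small and the correlation is high. Confidence is high in the direction and in the bounds, but the gain in this trial cannot be stated from the document.

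**What to change.** Before unblinding, specify for each outcome an ANCOVA of the post-treatment score on arm and pre-treatment score as the primary analysis. It should use the same pre and post scores as the planned change, with the visits named. Report the adjusted mean difference with its 95% confidence interval and two-sided p-value. Keep the t-test on change as a sensitivity analysis, and state the allocation ratio.

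Define the promised effect size, for instance as the adjusted difference divided by the pooled pre-treatment SD. The choice is a convention but must be named. With equal SDs and ρ = 0.7, a difference of 0.6 pre-treatment SD reads as 0.60 on that scale, 0.6/√0.6 = 0.77 on the change-score SD, and 0.6/√0.51 = 0.84 on the residual SD.

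The cost is about two sentences per outcome, one degree of freedom and a small variance inflation. The downside is a slightly wider interval and slightly less power if the slope proves to be near 1, or if the arms are very small and the correlation is high. If the planned arms are around 6 or smaller, or allocation is unequal, that trade-off should be weighed before the model is fixed.

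### Do the two unranked t-tests, PTSD and depression, need a named primary outcome and a multiplicity rule?

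*Combined protocol and SAP*

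**What the plan says.** The Statistical Analysis Plan section has three bullets. The first reads "We will conduct a t-test to evaluate difference in PTSD symptom changes from pre- to post-treatment between the active and placebo group". The second applies the same test to the other outcome: "We will conduct a t-test to evaluate difference in depression symptom changes from pre- to post-treatment between the active and placebo group". Each is followed by the same sentence, "We will calculate the effect size of the difference between the groups". The third bullet is of a different kind: "We will evaluate actigraphy data to provide descriptive information regarding treatment compliance".

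The design has two randomised arms: "Participant is randomized (assigned by chance) to a placebo (inactive) Re-timer or active Re-timer". The official title on the cover page is "Morning Light Treatment at Home to Reduce PTSD Symptoms"; it does not mention depression.

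Nothing in the document calls an outcome primary or secondary. It also gives no significance level, sidedness, testing order or adjustment for two tests, and no rule for calling the trial positive.

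**The concern.** Two tests with matching wording and no ranking leave one result without an agreed reading: PTSD not significant, depression significant. The plan does not say whether that would be a positive trial, so the reading could be settled after the data are seen. Only the actigraphy bullet is marked as descriptive, so depression appears to stand level with PTSD.

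If a significant result on either outcome were enough to say that the light treatment works, the chance of saying so wrongly, when neither outcome is affected, would exceed the level of a single test. All of the excess would come from depression-only results.

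**Working it through.** **Inputs from the document.** There are two between-group tests (first and second bullets). The actigraphy bullet adds no test. The plan states no error rate, so there is no figure to reproduce.

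**Assumptions, because the document gives none of these.** Each test is two-sided 0.05 (critical value 1.96, so 0.025 in the direction of benefit). Neither outcome is truly affected. Either result may support a single claim. The correlation between the two test statistics is taken from 0 to 0.9.

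**Independent tests.**

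- Either direction: 1 − (1 − 0.05)² = 1 − 0.9025 = 0.0975.
- Benefit only: 1 − (1 − 0.025)² = 1 − 0.950625 = 0.0494.

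**Correlated tests.** With (Z1, Z2) bivariate normal, the either-direction risk is 1 − P(|Z1| < 1.96, |Z2| < 1.96). The benefit risk is 1 − P(Z1 < 1.96, Z2 < 1.96). The excess is that risk minus 5% or 2.5%, and it equals the probability that depression alone is significant.

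| Correlation | Either direction | Excess over 5% (points) | Benefit only | Excess over 2.5% (points) |
|---|---|---|---|---|
| 0 | 9.75% | 4.75 | 4.94% | 2.44 |
| 0.5 | 9.07% | 4.07 | 4.54% | 2.04 |
| 0.7 | 8.35% | 3.35 | 4.17% | 1.67 |
| 0.8 | 7.81% | 2.81 | 3.90% | 1.40 |
| 0.9 | 7.04% | 2.04 | 3.52% | 1.02 |

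The lower end depends on where the range is cut: at correlation 0.95 the figures are 6.46% and 3.23%. The unstated sample size hardly matters. Simulated t-tests with an assumed 20 per arm gave 9.6% at correlation 0 and 7.9% at 0.8 (benefit 4.9% and 3.9%).

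**Which figure bears on the worry.** A significant difference favouring placebo cannot support a claim that the treatment works. The relevant column is therefore benefit only, with an excess of 1.0 to 2.4 points.

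**How the figure depends on the reading of the plan**, still with neither outcome affected:

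- PTSD decides and depression supports: the risk for the main conclusion is 5% (benefit 2.5%).
- Each test answers only for its own outcome: 5% (benefit 2.5%) for each statement, with no pooled claim to inflate.
- Either outcome may carry one claim for the treatment: the table applies.

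If PTSD symptoms truly improve, the third reading is not inflated either. The only false positive left is the depression test at its own level.

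**Which reading the text supports.** The title gives one aim, PTSD. The first bullet is PTSD. Each bullet concerns a difference in its own symptom measure, and no sentence joins the two into a verdict on the device. This fits the first two readings; the third has to be inferred from silence.

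**The case for a change.** The strongest case for a change is that a title is not a decision rule and bullet order is not a testing order. The plan shows in its third bullet that it can mark an analysis as descriptive, yet it gives depression the same inferential wording as PTSD. One sentence making PTSD primary, with depression confirmatory only after a significant PTSD result, would settle the depression-only case in advance. It would hold the familywise error at 5% and cost the PTSD test no power. If the sponsor already means this, the sentence only records it.

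Several parts of this stand. The omission is real, the arithmetic is right, and such a sentence would be harmless and tidy.

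It does not show that the plan as written leads to a wrong conclusion. The inflation needs a pooled claim that the document never makes. Both tests and both effect sizes are planned, so a depression-only result would sit beside a non-significant PTSD result. It would be a finding about depression that does not meet the aim in the title. Whether to control familywise error across two separate questions, with no success rule to protect, is a matter of judgement.

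The promised 5% would not follow from that sentence alone either. The plan names no scale for either outcome and does not say which visits are pre and post, although questionnaires are completed on days 8, 15, 22, 29 and 36. The guarantee holds only once those are fixed as well.

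**Conclusion.** No change to the plan follows. The document leaves out a label, and the natural way to supply it, PTSD as the main comparison and depression as supporting, is visible in the title and the order of the bullets. On that reading, or if each test is read as a statement about its own outcome, each conclusion keeps its own error rate.

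The excess risk of 1.0 to 2.4 percentage points for a false claim of benefit (2.0 to 4.75 in either direction) is an illustration. It rests on four assumptions: two-sided 0.05 for each test, no true effect on either outcome, a correlation between 0 and 0.9, and a rule that either result carries one claim. The document supplies none of them, and the last is the one on which the inflation turns.

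### Does the SAP need to define its actigraphy compliance measure, split it by arm and add the weekly schedule review?

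*Combined protocol and SAP*

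**What the plan says.** The compliance analysis is the third and last bullet of the Statistical Analysis Plan: "We will evaluate actigraphy data to provide descriptive information regarding treatment compliance". The two bullets before it, on PTSD and depression symptoms, each name the active and placebo groups. This one names no groups.

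The Study Protocol, under Weeks 2–6, gives the setting:

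- Treatment is unobserved: "A home sleep section with a daily morning light treatment the participant self-administers using the Re-timer light device".
- The comparator is an inactive version of the same device: "Participant is randomized (assigned by chance) to a placebo (inactive) Re-timer or active Re-timer".
- Monitoring goes on during treatment: "Participant continues to wear the wrist monitor that records motion and light". The same monitor is worn in Week 1, before any device is used: "A home sleep section with a wrist monitor that records motion and light".
- The visit calendar is "Weekly lab visits to complete questionnaires on days 8, 15, 22, 29, and 36". At these visits "we review the data from daily logs and wrist monitor", and staff also check whether the light schedule was kept. No form or score for that check is given.
- Use is meant to be daily. The lab visits include "training sessions on how to best use the Re-timer light device for light therapy every morning".

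**The concern.** With a device used at home, readers will ask two questions about compliance. After a null result: was the active device used? After a positive result: was use similar in the two arms? A summary with no stated signal, rule, denominator or arm split might answer neither.

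The choice of actigraphy adds to the worry. The monitor senses motion and light, not device use. Motion is recorded in the same way in both arms and may show when someone was up, but being awake is not a treatment session. Light is closer to the treatment itself, but the document does not state what the inactive device emits. If its sessions are harder (or easier) to detect than active ones, equal use could look unequal. Meanwhile the protocol plans a check on schedule adherence at the visits, and the SAP does not say what becomes of it.

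**Working it through.** The plan states no compliance figure, so there is nothing to reproduce. Three checks are possible.

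**1. The denominator (from the documents).** Treatment covers days 8 to 36, and use is daily. The document does not say whether a session is due on day 8, a visit day, or on day 36, the last visit.

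- Both days count: 36 − 8 + 1 = 29 mornings.
- One counts: 28.
- Neither counts: 27.

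For a participant with k treated mornings, the largest spread is k/27 − k/29. It grows with k, so over k = 0 to 27 it peaks at k = 27:

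- 27/27 = 100%
- 27/28 = 96.4%
- 27/29 = 93.1%
- Spread: 100 − 93.1 = 6.9 points

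One missed morning is worth 1/29 = 3.4 to 1/27 = 3.7 points. For a given count of treated mornings, a denominator applied alike to both arms rescales both by the same factor, at most 29/27 = 1.07. It cannot create a gap between arms with equal counts.

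**2. Unequal detection (every input assumed).** Suppose each morning is classed as session or no session. Let u be the true share of mornings with use, the same in both arms. Let s and s₀ be the probabilities that wrist light detects an active and a placebo session, and f the probability that ambient light is mistaken for a session. The share classed as sessions in the active arm is

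u[s + (1 − s)f] + (1 − u)f = f + u·s(1 − f),

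and likewise with s₀ for placebo. The false gap, active minus placebo, is u(s − s₀)(1 − f).

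Take u = 0.8, s from 0.3 to 0.9, s₀ from 0 to 0.9 and f from 0.1 to 0.5:

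- Highest: 0.8 × (0.9 − 0) × (1 − 0.1) = +0.648, or +65 points.
- Lowest: 0.8 × (0.3 − 0.9) × (1 − 0.1) = −0.432, or −43 points.
- At s = s₀ the gap is 0.

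The documents give none of these inputs. The lower end needs the inactive device to be detected three times as often as the active one (0.9 against 0.3). The range shows only that the gap follows whatever detection rates are assumed. It is not evidence that a gap exists.

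**3. The weekly review as an alternative source (texts side by side).** Day 8 opens treatment, so four of the five visits (days 15, 22, 29 and 36) can look back on treatment mornings, over 4 × 7 = 28 days. The schedule check is described directly after the review of the logs and the monitor, at the same visits, so it may rest partly on actigraphy. The listed log topics are activities, sleep, nightmares and medications; device use is not named. The document therefore does not show that an independent record of use exists.

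**The case for a change.** The best argument for a change is that a measure left undefined can be chosen after the results are known, and that fixing it costs little: a few sentences, one table by arm and a standard form at four existing visits. The factual part stands. The bullet does omit the signal, the rule, the denominator, the arm split and the weekly check, and the document does not establish that use is equally detectable in the two arms.

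The case for a revision is weaker.

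- No test, exclusion or adjustment in the SAP depends on compliance, so a late choice of summary cannot alter either treatment comparison.
- Silence on arms is not a decision to pool them. In a two-arm trial, a table by arm is the obvious way to describe compliance, and nothing in the bullet prevents it.
- Defining a rule would not make an inactive device visible to a light sensor. Any asymmetry is a property of the instrument, to be noted when the data are read.
- Taking the headline percentage from the weekly review would replace a recording with a check that may be self-report or may reuse the monitor data, and there is no ground for calling it more accurate. Tabulating disagreements between the two would still need an actigraphy rule for a treated morning, which is the very item missing.

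**Conclusion.** No change is needed. The omissions are real, but they are missing detail in a descriptive summary within a three-bullet SAP, and analysts can supply it sensibly: choose the signal and the denominator, use the Week 1 recording as each participant's reference, tabulate by arm, and note that light data may not show use of the inactive device. The only size the documents support is at most 6.9 points on one participant's percentage, and the two t-tests are untouched. The possible false gap between arms cannot be sized without the detection rates of the two devices.

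The conclusion assumes that compliance stays descriptive, as the bullet says. If it were later used to select participants or to adjust the treatment comparison, the definition would matter and would have to be fixed in advance.
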